1.0 Introduction

The overall goal of this study is to minimize negative consequences of Alzheimer's disease and related disorders (ADRD) diagnosis by enhancing the support systems of affected families through the provision of the Options Counseling-Health Education (OC-HE) intervention.

The primary objective is to evaluate the impact of OC-HE intervention on caregivers (caregiver burden) and patients (use of emergency care). The secondary objective is to evaluate the impact of the program through the proposed mechanisms of influence, enhanced social network composition (e.g., network size) and functioning (e.g., social support). In addition, we will assess intervention feasibility and acceptability to better understand intervention impacts and to inform future implementation from the perspectives of the participants, OC-HE interventionist, clinical care staff, and administrator at the Area Agency on Aging.

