Interventions are ongoing and flexible to meet the needs of the individual family. Following the standard OC protocol, the family receives an initial telephone intervention (previously in-person home visit, but occurred over the phone due to the pandemic) by the interventionist. During the initial call, the OC uses assessment tool to identify caregiver/family needs and develop family action plans to connect families directly to services and programs available in the area. The interventionist also conducts an assessment to determine educational needs, then conducts 2 additional monthly follow-up calls to adjust the care plans and to provide educational components appropriate at each point (3-month intervention). This program, thus, creates direct links between the medical clinics, HCBS, and family. The OC tailors the information provision to meet the needs of those receiving it by providing additional information as the time progresses, allowing the recipients to identify their concerns at the moment and presenting materials to address expressed concerns. Participants receive all educational materials and a brief overview of contents at the end of the 3-months intervention period, including the topics that may not have been covered in great detail during the intervention calls. The Area Agency on Aging provides continued support to individuals who need their services after the completion of the intervention.

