Mechanisms of Influence. The social network framework highlights the importance of enhancing network functions (e.g., social support) on health outcomes. Strong social support networks have been shown to be important for the well-being of caregivers and care recipients, and their ability to remain in the community. The intervention provides families 1) tangible, informational, and emotional support, 2) guidance on building strong support systems and effective communication, and 3) access service linking families directly to community-based resources. Through these activities, we intend to strengthen families' social networks to facilitate successful community living. In our prior study, families considered formal providers as important members of their caregiving support systems, suggesting the important role Area Agency on Aging staff can play in this mechanism. In this study, we are systematically examining the compositional and functional characteristics of social networks, that are theorized to influence patient and family outcomes. We will assess the mechanisms of influence using the social network measures specifically developed for dementia caregiving studies that assess social interactions specific to caregiving in addition to general support. Understanding the mechanisms through which intervention improves outcomes will provide a framework to optimize support for patients and their families across all stages of the illness.

Revised Data Analysis Plan

Network composition: Network members are enumerated based on participation in caregiving activities and provision of support to caregivers at baseline. In 3- and 6-month assessments, participants indicate changes in their networks (e.g., indicate those who are no longer part of support network, add new support providers). We will develop network composition measures including network size and proportion/number of family, non-family/friends, professional providers, live locally, gender, age groups (e.g., same/older/younger generations).

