Perceived support: At each assessment, the participants report their relationships with each network member (e.g., who provides emotional support? Who helps you provide direct care? Who participates in discussions to make care decisions) to assess network functions. Levels of support can be determined by taking an average support levels among family, non-family, professionals, for each type of support (e.g., emotional, informational, instrumental, direct care, care decision making).

Social engagement: Participants identify network members with whom they engage in social activities to assess how the network functions as a context for social engagement.

At the patient level, generalized linear models (GLM) with an appropriate link function (e.g., the identical link for continuous outcomes, the logit for dichotomous outcome, and the log link for count outcomes) will be used to assess associations between the caregiver and patient outcomes and network composition and network functions. In particular, a set of the composition measures will be considered as independent variables to each outcome in a GLM. Similarly, a set of network functions (e.g., change between baseline and 3-month) will be included to assess the association with each outcome at 6-month in a GLM.

Follow-up analyses

Once we identify network functions that are important for the caregiver and patient outcomes (e.g., emotional support, provision of direct care support) are identified in the main analyses, we will be able to conduct dyad-level analyses to identify the whole network characteristics (e.g., network size, homogeneity), network member characteristics (e.g., gender, relationships, live locally), as well as relationship characteristics (e.g., presence of trust, duration of relationship) that may contribute to such positive network functions.

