At the dyadic-level, a logistic regression model will be fitted for each outcome (e.g., presence of emotional support, provision of direct care support) using generalized estimating equations with the exchangeable correlation structure to account for the clustering of the network members within the respondents' networks. Both respondent-level (e.g., gender, relationship to care recipient) and network member-level covariates (e.g., family member of the care recipient, age, whether living locally) will be considered in these models. To assess the impact of changes in network functions, differences between baseline and 3-month network functions (e.g., change in support provision) will be used as independent variables to the outcomes at 6-months.

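### No model in the supplied SAP names randomised arm or baseline values, so as written it does not estimate the effect of OC-HE on networks or any indirect effect through them

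*SAP*

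**What the plan says.** The Protocol (1.0 Introduction) states: "The secondary objective is to evaluate the impact of the program through the proposed mechanisms of influence". It names two such mechanisms, network composition (network size is its example) and network functioning. The SAP (Mechanisms of Influence) repeats the aim: "We will assess the mechanisms of influence using the social network measures specifically developed for dementia caregiving studies".

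The SAP then describes three models.

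- Composition GLM (Revised Data Analysis Plan): "a set of the composition measures will be considered as independent variables to each outcome in a GLM".
- Function GLM (same section): "a set of network functions (e.g., change between baseline and 3-month) will be included to assess the association with each outcome at 6-month".
- Dyad-level logistic GEE (Follow-up analyses): the response is whether a network member provides a given kind of support. The covariates are "Both respondent-level (e.g., gender, relationship to care recipient) and network member-level covariates", each group illustrated by examples. For change, "differences between baseline and 3-month network functions (e.g., change in support provision) will be used as independent variables to the outcomes at 6-months".

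The purpose given for the two patient-level GLMs is to assess associations. The functions that those models pick out as important are the ones carried into the dyad-level analyses.

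**The concern.** A program effect that runs through networks has two links: arm to network, and network to outcome. The SAP specifies only the second, and without the randomised comparison. Followed as written, it can show which network features go with lower burden or less emergency care, but not whether OC-HE altered those features.

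A second, smaller issue concerns the network-to-outcome link. Change from baseline to 3 months is the only predictor example given, and no baseline term is named beside it. Change is normally negatively related to its own starting value, so the slope can pick up baseline differences. It can also pick up any effect of OC-HE on burden by another route. Because the function results select what is studied at dyad level, an imprecise or biased slope carries forward.

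**Working it through.** **1. Model content, side by side.**

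| Model | Response | Predictors named | Arm | Baseline outcome | Baseline network level |
|---|---|---|---|---|---|
| Composition GLM | Caregiver and patient outcomes, time point not stated | Composition measures | Not named | Not named | Not named |
| Function GLM | 6-month outcomes | Functions, e.g. 0-3 month change | Not named | Not named | Only inside the difference |
| Dyadic GEE | Support from a network member; 6-month outcomes for the change analysis | Respondent and member covariates (examples), change | Not named | Not named | Only inside the difference |

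Estimating the effect of OC-HE on networks needs a network measure as response and arm as predictor. Composition is never a response. Functions are a response only in the GEE, where arm is not named. No indirect effect or mediation method is given.

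**2. Can the function GLM reveal mediation?** Illustration with assumed standardised coefficients, n=80, 4,000 runs: network change truly affects the outcome (-0.4). If arm has no effect on networks, the indirect effect is zero, yet the change-only model is significant in 89% of runs. If arm shifts networks by 0.5, it is significant in 91%. The model cannot tell the two apart.

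**3. Anchors for the change-score illustration.** Protocol 5.0 (Sample) gives 106 enrolled, 25% attrition, 40 per group, 84% power and 4 points. 106 x 0.75 = 79.5, about 80. The SD is not stated. Back-solving with a two-sided 5% normal approximation, SD = 4 / [(1.960 + 0.994) x sqrt(2/40)] = 6.05; the t-based value is 5.98. So SD 6 is used. If 4 points per 3-month period accumulate to 8 by 6 months, the same formula gives 12.11.

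**4. Assumed model.** S0 and S3 are support at baseline and 3 months, B0 standardised baseline burden, B6 6-month burden, e independent noise:

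- S3 = 0.6 S0 + 0.8e + a x arm
- B6 = 6(0.7 B0 + 0.714e) + beta x support term + d x arm
- corr(S0, B0) = r

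Cov(S3 - S0, S0) = 0.6 - 1 = -0.4, and the variance of change is 0.16 + 0.64 = 0.80 before any arm effect. With no true support effect (beta = 0), the change-only slope is

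(-6 x 0.7 x 0.4 x r + 0.25 x a x d) / (0.80 + 0.25a²) = (-1.68r + 0.25ad) / (0.80 + 0.25a²).

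A positive slope makes support look harmful; a negative one makes it look beneficial.

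| r, a, d | Slope from formula | Simulated false positives, change-only |
|---|---|---|
| 0, 0, 0 | 0 | 5.3% |
| -0.1, 0, 0 | 0.168/0.80 = +0.21 | 6.0% |
| 0, 0.3, -2 | -0.15/0.8225 = -0.18 | 5.6% |
| 0, 0.5, -2 | -0.25/0.8625 = -0.29 | 7.6% |
| -0.3, 0.5, -2 | 0.254/0.8625 = +0.29 | 7.0% |
| -0.3, 0.5, -4 | 0.004/0.8625 = 0.00 | 4.7% |
| -0.3, 0, 0 | 0.504/0.80 = +0.63 | 13.1% |
| -0.5, 0, 0 | 0.84/0.80 = +1.05 | 29.4% |
| 0, 0.5, -4 | -0.50/0.8625 = -0.58 | 11.8% |
| 0, 0.8, -4 | -0.80/0.96 = -0.83 | 21.3% |

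With S3, S0, B0 and arm in the model, the rate is 4.6% to 5.4%. Arm alone is not enough: in the separate model of step 2, with baseline outcome driving network change, false positives were 13.8% without arm, 13.8% with arm, and 5.0% with arm and both baselines.

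**5. Precision.** Take a true slope of -1.8 points per SD, no confounding, and burden responding to raw change. Change-only: SE about 6/sqrt(80 x 0.80) = 0.75, ratio 1.8/0.75 = 2.4, simulated power 65% with no bias (slope -1.81). Adjusted: residual SD 6 x 0.714 = 4.28, SE about 4.28/(0.8 x sqrt(75)) = 0.62, ratio 2.9, simulated power 82%.

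**The case against.** Four objections carry weight.

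- *Arm is not excluded.* The GEE covariates are given as examples and the composition measures are only to be considered, so an analyst could add arm. A reader might infer that the SAP rules arm out. It does not; it leaves arm unnamed. Even so, arm as an optional covariate in the GEE would not give an indirect effect.
- *The arm models may be elsewhere.* Protocol 2.0 places the study protocol in an appendix that was not supplied, and the supplied SAP contains no between-arm model for burden either, so arm comparisons may well be kept there. A reader might conclude that the trial as a whole cannot show whether OC-HE changed networks. The documents do not support that; the gap is established for this SAP only. Any such models would still need aligning with the revised 3-month intervention, since Protocol 7.0 describes an initial visit and five monthly calls.
- *The bias is assumed.* No document gives a correlation, a path, a support SD or the -1.8 slope. The 4-point direct path lets the whole planned effect bypass networks, and milder inputs give little inflation. A reader might take 29% as this trial's error rate, or take change scores to be invalid. Neither follows: without confounding, and with burden responding to raw change, the change score is unbiased. The SD matters too. At SD 10 with the same 4 points, the arm-path rates fall to 7%-11%; the baseline-correlation rates do not depend on the SD, because slope and SE scale together.
- *This is a Stage 1 study that promises associations.* That is fair as to importance, but the objective and the SAP's own mechanism statement promise more than association.

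The coding of dyadic change is not counted as an error. If change in a yes/no support item were a numeric difference, zero would merge ties that always supported with ties that never did, and members added later (participants "indicate those who are no longer part of support network, add new support providers") would have no baseline status. But the SAP does not say that it will be coded that way, and no effect has been shown.

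**Conclusion.** The point holds for the SAP as supplied. None of its three models names randomised arm, the baseline outcome or the baseline network level. Followed as written, it estimates neither the effect of OC-HE on network composition or functions nor an indirect effect, although impact through these mechanisms is the secondary objective. This rests on reading the models, not on simulation, and is subject to the unseen appendix.

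The change-score issue is secondary, and its size is illustrative. The power gap of about 65% against 82% assumes n=80, SD 6, a -1.8 slope, no confounding and a raw-change response. False positives range from roughly 5% to 29% depending on assumed paths, in either direction, against about 5% adjusted. The change should be made before analysis; it does not call the trial itself into question.

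**What to change.** Add to the SAP:

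> For each measure on a short prespecified list of network composition measures (including network size) and network functions: (a) the 3-month value will be modelled on randomised arm and its baseline value; (b) the 6-month outcome will be modelled on the 3-month value, its baseline value, the baseline outcome and arm; (c) the indirect effect will be reported with a bootstrap 95% CI (standardisation-based for logit and log links) and labelled exploratory, because unmeasured network-outcome confounding remains. The dyadic GEE will include arm.

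If arm models already exist in the protocol appendix, cite them and align them with the revised schedule, which the SAP overview describes as "to provide educational components appropriate at each point (3-month intervention"). The time order needed is already there: intervention to 3 months, network at 3 months, outcome at 6 months.

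Costs:

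- No new visits. A baseline window for emergency-care use must be defined from the medical-record data (Protocol 6.1).
- Three degrees of freedom per single-measure model at n=80 (78 to 75).
- If burden responds only to raw change, the baseline-network term costs power: 89% with change, baseline burden and arm, 82% once it is added (same illustration).
- Modest power. At n=80, for arm effects on the network of 0.3 / 0.5 / 0.8 SD, model (a) has 40% / 78% / 99% and the indirect effect 33% / 63% / 83%; at n=60 the indirect effect has 17% / 46% / 66%. Hence the short list and the exploratory label.

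Optional: code dyadic support between baseline and 3 months as kept, gained, lost or never, with a separate category for ties added later, and state how dropped ties are handled.

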6.1 HIPAA Authorization

Because we have access to health data through the electronic medical record and because we are collecting some data through the electronic medical record (MoCA and use of medical services), all research team members have completed HIPAA training through the University of Iowa Hospitals and Clinics Human Resources.

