7.0 Study Intervention

Intervention Description

The intervention consists of two parts, Options Counseling (OC) and Health Education (HE). The OC part includes family assessment, counseling and provision of emotional support, access assistance, and development of independent-living plans (care plans) using the Iowa's Heritage Area Agency on Aging database. The HE part includes post-diagnosis family education. Options Counselor (OC) is trained to implement these tasks through using motivational interviewing techniques. We developed seven modules of the HE toolkit based on an extensive literature review on unmet needs of families receiving diagnosis of dementia, experiences of Options Counselors, and expert reviews by experienced staff members at the local Alzheimer's Association.

Through the OC-HE intervention, we aim to minimize caregiver burden through enhancing the social support network system of the participants by providing direct access to community-based programs as well as to the Options Counselor who provides emotional support and instructions on how to form strong support networks. Lower burden and better support are associated with better patient outcomes, thus, we will also evaluate whether PWDs whose caregivers receive OC-HE intervention would use emergency or urgent medical services to a lesser extent.

Each intervention encounter will occur in a setting of the participant's choosing. Typically, the initial visit is in the home of the participant (caregiver) and involves just the participant and the Options Counselor. However, the participant is able to invite whomever they choose to come to the meeting, including the PWD. The participant may choose to have the meeting at different location if the person they are caring for lives with them and they do not want to introduce the information in this manner. Although it is preferable to have this initial visit in person, the meeting can be done via phone call or virtually through a web-conferencing if participant desires so. Normally, each home visit, or face to face meeting, lasts around 1.5 hours, however, because of the addition of the Health Education component in this particular study, we

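### The network mechanism models do not fix the time window for emergency care or adjust for earlier emergency use, so an early emergency can pass for a network effect

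*SAP*

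**What the plan says.** The SAP (Revised Data Analysis Plan) sets out two kinds of patient-level generalized linear model.

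- **Network functions:** "network functions (e.g., change between baseline and 3-month) will be included to assess the association with each outcome at 6-month in a GLM".
- **Network composition:** "a set of the composition measures will be considered as independent variables to each outcome in a GLM". Neither the wave of the composition measure nor that of the outcome is given.

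The Follow-up analyses repeat the lag: "differences between baseline and 3-month network functions (e.g., change in support provision) will be used as independent variables to the outcomes at 6-months".

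Protocol section 1.0 names the outcomes in the primary objective: "evaluate the impact of OC-HE intervention on caregivers (caregiver burden) and patients (use of emergency care". Section 7.0 asks whether patients in the intervention arm would "use emergency or urgent medical services to a lesser extent". Section 6.1 gives the source: "we are collecting some data through the electronic medical record (MoCA and use of medical services".

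On scale, the SAP allows the identity link, "the logit for dichotomous outcome, and the log link for count outcomes", but assigns no outcome to any link. On the network, participants at 3 and 6 months can "indicate those who are no longer part of support network, add new support providers". Covariates are named for the dyad-level models only.

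The SAP's Mechanisms of Influence section says that the network analyses are meant to show how the intervention improves outcomes.

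**The concern.** Network change is not randomised. What puts the proposed cause before its effect is the lag: change over months 0-3, outcome at 6 months. Caregiver burden is a score with a value at the 6-month survey. Emergency use builds up over an interval, so the lag means little until that interval is stated.

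The model is exposed under either open reading of the window.

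- **Months 0-6.** An emergency at month 2 may bring relatives or professionals into care. It then alters the 3-month network measure and is also part of the outcome.
- **Months 3-6.** Nothing is counted twice. But patients at higher risk have more emergencies both before and after month 3, so an early emergency that changed the network also predicts the later outcome. The model has no term for it.

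In the composition models, network and outcome may come from the same wave, with nothing to show which came first.

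At stake is the secondary objective, whether networks are the route to better outcomes. If the network measure rises after an emergency, the artefact makes more support look linked to more emergency use. That could mask a benefit or suggest harm.

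**Working it through.** **Plan figures.** The documents give no figure for the mechanism models. The only power statement (Protocol section 5.0, about 84% for burden) does not bear on this point. The analysable sample does: 106 × 0.75 = 79.5, which agrees with the stated 80.

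**Inputs.** n = 80 comes from the Protocol. Visit rates, network response and between-patient variation are assumptions, because the documents give none.

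**Model.** V03 and V36 are visits in months 0-3 and 3-6, each Poisson with mean λF, where F is patient risk with mean 1 and variance v (0 = equal risk, 1 = unequal risk). Network change is X = g·V03 + e, with e standard normal. X has no effect on V36. Three Poisson regressions are compared:

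- (a) log E[V03 + V36] = b0 + b1·X
- (b) log E[V36] = b0 + b1·X
- (c) log E[V36] = b0 + b1·X + b2·V03

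The correct rate ratio, exp(b1), is 1 for the effect of X on later visits.

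**Why (b) can still fail.** Cov(V03, V36) = λ²v and Var = λ + λ²v, so the correlation is λv/(1 + λv). With v = 0 it is 0. With v = 1 and λ = 0.25 it is 0.25/1.25 = 0.20. X carries V03, so X predicts V36.

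**Grid 1** (up to 1,500 runs per cell; response of g per visit; robust standard errors when v = 1). Results at λ = 0.25 visits per 3 months, as median rate ratio per unit of X, with the share of runs at p < 0.05:

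| v | g | (a) 0-6 count | (b) 3-6 count | (c) 3-6, adjusted |
|---|---|---|---|---|
| 0 | 0 | 1.00 (4.5%) | 1.00 (4.9%) | 1.00 (4.9%) |
| 0 | 0.25 | 1.14 (13.1%) | 1.01 (5.3%) | 1.01 (4.9%) |
| 0 | 0.5 | 1.26 (33.0%) | 1.00 (5.4%) | 1.00 (5.5%) |
| 0 | 1 | 1.47 (79.6%) | 1.00 (5.3%) | 1.00 (4.9%) |
| 1 | 0 | 1.00 (8.2%) | 1.00 (9.1%) | 1.01 (9.7%) |
| 1 | 0.25 | 1.20 (20.5%) | 1.08 (9.9%) | 1.02 (9.0%) |
| 1 | 0.5 | 1.41 (48.5%) | 1.13 (12.1%) | 1.01 (8.6%) |
| 1 | 1 | 1.68 (90.0%) | 1.21 (19.7%) | 1.01 (10.0%) |

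Over λ = 0.1 to 0.5 and g = 0.25 to 1:

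- (a) gives 1.13-1.57 with equal risk and 1.15-1.68 with unequal risk.
- (b) gives 0.99-1.01 with equal risk and 1.01-1.28 with unequal risk (false positives 10-52%).
- (c) with unequal risk gives 0.99-1.02 (false positives 7-14%). With no network response at all the false-positive rate is 6-13%, so what remains above 5% comes from robust standard errors in a small sample, not from bias.

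**Grid 2** (response tied to any early visit; λ = 0.15 and 0.30; response 0.25-1.0 SD):

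- (a) gives about 1.1-1.6, with false positives of about 9-74%.
- (b) gives about 1.0 with equal risk and 1.03-1.16 with unequal risk.
- (c) gives about 1.00-1.03.

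At a response of 0.1 SD with equal risk, (a) gives only 1.04-1.06, with 5% false positives.

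**Yes/no version.** With any visit as outcome, a logit link, equal risk and responses of 0.5-1.0 SD, months 0-6 give odds ratios of 1.32-1.75 (false positives 19-64%). Months 3-6 give 0.99-1.01 (4-5%). The problem does not depend on the outcome being a count.

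**The case against.** A reader might infer that emergency care is a count over the full six months, so that the overlap is a fact of the plan. The documents do not support that. They speak only of use of emergency care, list count as one possible outcome type, and tie no link to this outcome. With surveys at baseline, 3 and 6 months, an outcome at 6 months could as well cover the time since the 3-month survey, which leaves no overlap. The window may also be defined elsewhere: Protocol section 2.0 refers to a study protocol in an appendix, and the baseline interview (Appendix L) is not in the text supplied. This stands: overlap is permitted, not established.

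The direction of bias is not established either. The SAP says support levels can be averaged within groups of network members, and an average need not rise when helpers are added. This also stands.

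The size depends on the assumed response, and small responses give little bias. The equal-risk result for months 3-6 also flatters the restricted window, because early and late visits are then independent. Both stand, and the ranges above show them.

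Finally, the SAP says association, and this is a secondary objective in a Stage 1 study. That lowers the stakes but does not remove the point, because the SAP gives these analyses a mechanism purpose.

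**Conclusion.** The point holds in a conditional form. In the documents supplied, neither the unit nor the window of emergency care is fixed, the patient-level models name no adjustment for earlier emergency use, and the composition models have no time order. This is more than a missing detail, because the model as written is exposed whichever window is chosen: to double counting from baseline, or to confounding by earlier emergencies after month 3.

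For 0.15-0.30 visits per 3 months and a response of 0.25-1.0 SD to any early visit, the false rate ratio is about 1.1-1.6 for a 0-6-month count and 1.03-1.16 for a 3-6-month count with unequal risk. It is about 1.00-1.03 once earlier visits are in the model. These figures illustrate what could happen; they do not estimate the bias in this trial. They assume that emergencies raise the network measure. If emergencies leave it unchanged there is no such bias, and if they lower it the bias reverses.

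**What to change.** In the SAP's patient-level models:

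1. State whether emergency care is a count or any visit. Define it as visits dated after the participant's 3-month survey and up to the 6-month survey. For a count, use log days in that window as offset and robust standard errors.
2. Enter emergency use before the 3-month survey as a covariate. The window alone is not enough when patients differ in risk.
3. In the composition models, use composition at baseline or 3 months, with outcomes after 3 months.

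The cost is SAP wording, provided that service use taken from the medical record carries visit dates, which the documents do not say but which is likely. The downside is fewer events and wider intervals in the mechanism models. Robust standard errors with about 80 participants ran at 7-14% false positives under unequal risk in the check above, so borderline p-values from these models should be read with caution.

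### Used alone, the baseline-to-3-month difference in the dyadic models gives constant supporters and never-supporters the same code and can greatly understate how gaining or losing support relates to 6-month support

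*SAP*

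**What the plan says.** The SAP's Follow-up analyses section moves to the level of the individual network member. There, "a logistic regression model will be fitted for each outcome (e.g., presence of emotional support, provision of direct care support"). Members of one respondent's network are treated as a cluster, by GEE with an exchangeable working correlation. The outcome is therefore yes/no for each member.

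The change analysis is one sentence. It states that "differences between baseline and 3-month network functions (e.g., change in support provision) will be used as independent variables to the outcomes at 6-months". No coding of change is given, and neither the baseline nor the 3-month level of the function is named as a companion term. Of the covariates, the SAP says that "network member-level covariates (e.g., family member of the care recipient, age, whether living locally) will be considered in these models"; the respondent-level list is also given by example only.

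Two descriptions under Perceived support bear on what a network function is. The questions put to participants ask them to name members ("who provides emotional support? Who helps you provide direct care"), which points to a yes/no value per tie. The same paragraph adds that "Levels of support can be determined by taking an average support levels among family, non-family, professionals, for each type of support", which is an averaged quantity for a group of members.

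**The concern.** For a yes/no tie, the 3-month value minus the baseline value takes three values, but there are four histories. Gained is +1 and lost is -1. Kept (yes, yes) and never (no, no) are both 0. If the outcome is the same function at 6 months, one would expect kept ties to be among the likeliest to be present and never ties among the least likely, yet a model with only the difference gives them the same predicted odds.

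The difference also carries a hidden constraint. It forces the coefficient for baseline status to be the negative of the coefficient for 3-month status. If gaining support by 3 months predicts support at 6 months, the model must also say that having given support at baseline predicts its absence.

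What is at stake is the SAP's only dyad-level analysis of change. Its purpose is to show whether shifts in who gives support carry forward to 6 months, and mechanism is a stated secondary objective (Protocol Section 1.0).

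**Working it through.** The documents state no figure for this analysis, so there is none to reproduce. All rates below are assumptions. The check covers members present at both baseline and 3 months; members who join or leave ("indicate those who are no longer part of support network, add new support providers") are a separate matter.

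**Structure.** Let Y0, Y3 and Y6 be 0/1 for whether a member gives a stated kind of support at baseline, 3 and 6 months, and let D = Y3 - Y0.

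- Difference model: logit P(Y6 = 1) = a + b·(Y3 - Y0) = a - b·Y0 + b·Y3.
- Two-wave model: logit P(Y6 = 1) = a + b0·Y0 + b3·Y3.

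The first is the second with b0 = -b3 imposed. Adding gender, age, relationship or living locally does not lift that constraint; adding Y0 does.

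**Assumed inputs.**

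| History | Y0, Y3 | D | Share of ties | P(Y6 = 1) | Odds |
|---|---|---|---|---|---|
| Never | 0, 0 | 0 | 40% | 0.10 | 0.111 |
| Kept | 1, 1 | 0 | 40% | 0.85 | 5.667 |
| Gained | 0, 1 | +1 | 10% | 0.70 | 2.333 |
| Lost | 1, 0 | -1 | 10% | 0.20 | 0.250 |

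**Contrasts between histories.**

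- Gained versus never: 2.333 / 0.111 = 21.
- Lost versus kept: 0.250 / 5.667 = 0.044; inverted, kept versus lost is 22.7.
- Baseline status at fixed 3-month status: lost versus never 0.250 / 0.111 = 2.25; kept versus gained 5.667 / 2.333 = 2.43.

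**Fitted models** (logistic regression weighted to the shares above).

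- Two-wave model: odds ratio (OR) 21.8 for 3-month status, between 21 and 22.7, and 2.35 for baseline status, between 2.25 and 2.43.
- Difference model: OR 3.0 per unit. The implied baseline OR is 1 / 3.0 = 0.33, the opposite direction from 2.35.

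**Does the result depend on the mix of stable ties?** With gained and lost held at 10% each:

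| Never / kept | P(Y6 = 1) at D = 0 | Gained versus D = 0, OR | Difference-model slope, OR |
|---|---|---|---|
| 50% / 30% | (0.5×0.10 + 0.3×0.85) / 0.8 = 0.381 | 3.79 | 3.16 |
| 40% / 40% | (0.4×0.10 + 0.4×0.85) / 0.8 = 0.475 | 2.58 | 3.01 |
| 30% / 50% | (0.3×0.10 + 0.5×0.85) / 0.8 = 0.569 | 1.77 | 3.03 |

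The contrast against D = 0 halves although no history's probability has changed. The single slope hardly moves; even mixes of 70/10 and 10/70 give only 4.4 and 3.6.

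**Other assumptions.**

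- Probabilities of 0.10 never, 0.90 kept, 0.70 gained and 0.30 lost, with 15% gained and 15% lost: OR 2.3 to 2.9 for the difference alone, against 21.0 with baseline added, as the kept share of stable ties runs from 10% to 90%.
- The same pattern in simulated GEE fits with exchangeable correlation (80 respondents with 6 members each, 60 replicates): 2.3 to 2.7 against about 19.
- Y6 depending on Y3 only (0.90 versus 0.10): 9.0 to 16.2 against 81.
- Ties reflecting only a stable propensity, exchangeable over the three waves: log-OR exactly 0 for the difference alone, against 0.83 to 1.61 with baseline added.

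**The case against.** The strongest reply is that the SAP does not say what this concern needs it to say.

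- Yes/no coding is explicit only for the outcome. For the predictor the text says differences in network functions, and the Perceived support paragraph also offers group averages. A respondent-level change in an averaged score is a permitted reading, and the exact collision does not arise there. This stands as a limit. It does not remove the point: the example attached to the sentence is a change in support provision within a member-level model, and an average over a group does not describe one tie. A change score without its starting level also has a similar weakness, since stable-high and stable-low respondents both score near 0.
- Baseline adjustment is not ruled out. With baseline status in the model, the difference term becomes the association with 3-month status given baseline, which is interpretable. This stands too. A reader might infer that the SAP omits baseline by design; the documents are silent.
- The predictor and the outcome need not be the same function. True; the size shown applies when they are.
- A reader might infer that the planned odds ratio is driven by the mix of stable supporters and non-supporters, or that it means nothing. Neither follows. The strong dependence belongs to contrasts against the D = 0 group, which a single linear difference term does not report. The slope is fairly stable (3.0 to 3.2 over the mixes tabulated) and is a definable, constrained contrast. Its faults are attenuation and the wrong-signed implied baseline effect.

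**Conclusion.** The concern holds in limited form. Read naturally, the sentence on change pools kept and never ties at 0 and forces equal and opposite coefficients for the two waves. For a yes/no tie both facts are arithmetic. When predictor and outcome are the same function, the slope is hard to interpret and can be far too small: about 3.0 per unit against about 22 for 3-month status under the assumed rates, with an implied baseline OR of 0.33 where the two-wave model gives 2.35.

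Those sizes rest on invented transition rates; only their direction and rough scale should be carried away. The conclusion also rests on two readings that the SAP does not spell out: that change is measured per tie, and that baseline status is left out.

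A reader might go on to infer that the trial's result is at risk. The documents do not support that. This is a follow-up mechanism analysis, conditional on what the main analyses identify, and it does not enter the comparison of study groups on caregiver burden or emergency care. It is still worth correcting, because the better method uses the same data at little cost.

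**What to change.** In the SAP's Follow-up analyses, replace the difference with a four-level transition factor for each member and function (never, gained, lost, kept), and report gained versus never and lost versus kept.

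Alternatively, enter baseline and 3-month status as two separate terms. That reproduces the four-level factor only if their interaction is included; without it, gained versus never is forced to equal kept versus lost.

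State whether change is measured per tie or as a respondent-level average; if the latter, include the baseline level with the change score. Leave the GEE and its exchangeable structure as they are.

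The cost is a short change of wording, one more parameter per model for two separate terms or two more for the four-level factor, and some loss of precision. No new data are needed.
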